4.1.5 Secondary Endpoints 3 – 5: Solia S Lead Measurements

There are no formal hypotheses for secondary endpoints 3 – 5. Descriptive statistics, including mean, standard deviation, min, and max will be provided for each lead measurement at the visits of interest.

For analysis of secondary endpoint 3 (Solia S LBB pacing threshold at 3-, 6-, and 12-months post-implant), ITT population subjects with threshold data available at the visit of interest will be included. Subjects for which a pacing threshold was not available at a given visit will be excluded from the analysis.

For analysis of secondary endpoint 4 (Solia S LBB R-wave sensed amplitude at 3-, 6-, and 12-months post-implant), ITT population subjects with R-wave sensed data available at the visit of interest will be included. Subjects for which a R-wave sensed amplitude was not available at a given visit and pacing dependent subjects for which value could not be obtained will be excluded from the analysis.

For analysis of secondary endpoint 5 (pacing impedance at 3-, 6-, and 12-months post-implant), ITT population subjects with impedance data available at the visit of interest will be included. Subjects for which a pacing impedance was not available at a given visit will be excluded from the analysis.

4.2 Analysis of Additional Data of Interest

Additional data of interest will be reported for the relevant ITT analysis population (i.e., safety additional data of interest will utilize the same ITT population as primary endpoint 1; lead implant information will utilize the same ITT population as primary endpoint 2; remaining additional data of interest will utilize same ITT population as secondary endpoints

1 and 3 -5). For each analysis, only subjects with the data of interest available at implant or visit will be included. Subjects for which data is not available will be excluded from the analysis.

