#### 9.3 Clinical Events Committee

A Clinical Events Committee (CEC) will be established consisting of four independent physicians familiar with cardiac rhythm management devices. All adverse events reported by sites that may be related to 1) the Solia S lead implanted or attempted to be implanted in the LBB area, and/or 2) implant procedures, will be adjudicated by the CEC. The CEC may also evaluate and categorize LBBAP characteristics. Source documents supplied to the CEC will have confidential subject identifiers and site identifiers redacted.

The CEC is charged with the development of specific criteria used for the categorization of clinical events and clinical endpoints in the trial. Explicit rules outlining the minimum amount of data required, and the algorithm followed to classify study endpoint-related clinical events will be established.

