2.2.3 Additional Data of Interest

Additional information is collected to characterize the study population, implanted system, and progress of the clinical investigation. These include demographics, medical history, cardiovascular medications, ECG characteristics, implanted device information, device programming, Home Monitoring transmission success, non-Solia S LBB area related adverse events, reasons for inability to place or achieve capture with Solia S in LBB area, revisions to implanted systems, results for returned product analysis, compliance to protocol, and change in QOL scales.

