3.1 Statistical Methods

Descriptive statistics will be used to present and summarize the data collected in the clinical study. Frequency distributions (counts and percentages) and cross tabulations will be

presented for discrete variables. Means, standard errors, and ranges will be presented for continuous variables. Proportions will be calculated using known non-missing values. All statistical tests and/or confidence intervals will be performed at $\alpha = 0.05$ (2-sided).

For reporting of adverse events, descriptive statistics that describe the percentage of subjects experiencing an adverse event and rate of adverse event as events per subject-year will be provided. The total number of ITT subjects and cumulative duration of follow-up completed for the subjects as of the date of the report will be utilized to calculate the descriptive statistics.

Analysis of SADE-free rates for Solia S and procedure related events will be based on Clinical Events Committee (CEC) adjudicated event data. Analysis of the rest of the endpoints will be based on site-reported data.

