3.2 Analysis Populations

All clinical data will be analyzed based upon the pre-defined analysis populations as outlined in Table 1. Additional analysis population considerations for specific analysis are included within the analysis method details (Section 4).

Table 1: Study Analysis Populations

Analysis Population	Definition
Intent-to-Treat (ITT) – Primary Endpoint 1 (Safety), Secondary Endpoint 2	This ITT population is defined as 
 • all enrolled subjects (subjects with successfully implanted Solia S in the LBB area) and • subjects with an unsuccessful implant attempt of the Solia S in the LBB area who had a qualifying primary safety endpoint event prior to their exit from the study.
Intent-to-Treat (ITT) – Primary Endpoint 2 (Efficacy)	This ITT population is defined as 
 • all enrolled subjects (subjects with successfully implanted Solia S in the LBB area) and • subjects with an unsuccessful implant attempt of the Solia S in the LBB area.
Intent-to-Treat (ITT) – Secondary Endpoint 1 (QOL), Secondary Endpoints 3-5	This ITT population is defined as 
 • all enrolled subjects (subjects with successfully implanted Solia S in the LBB area)

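### Additional safety tables use the primary endpoint 1 set, so adverse events after a failed implant attempt are left out unless the subject also had a qualifying primary safety event

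*SAP*

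**What the plan says.** SAP 4.2 assigns each kind of additional data to an analysis set. For safety, "safety additional data of interest will utilize the same ITT population as primary endpoint 1". For implant data, the same sentence says "lead implant information will utilize the same ITT population as primary endpoint 2".

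SAP 3.2, Table 1, defines three ITT sets:

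- **Primary endpoint 1 and secondary endpoint 2:** "all enrolled subjects (subjects with successfully implanted Solia S in the LBB area") plus "subjects with an unsuccessful implant attempt of the Solia S in the LBB area who had a qualifying primary safety endpoint event" before leaving the study.
- **Primary endpoint 2:** all enrolled subjects plus every subject with an unsuccessful attempt.
- **Secondary endpoints 1 and 3 to 5:** enrolled subjects only.

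The one adverse event item in the list of additional data in SAP 2.2.3 is "non-Solia S LBB area related adverse events".

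SAP 3.1 gives a general rule for adverse event percentages and rates per subject-year. Its denominator is "The total number of ITT subjects and cumulative duration of follow-up completed for the subjects". It does not say which ITT set is meant.

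Protocol 9.3 sends to the Clinical Events Committee (CEC) "All adverse events reported by sites that may be related to 1) the Solia S lead implanted or attempted to be implanted", and also events that may be related to implant procedures.

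**The concern.** A subject with a failed attempt has undergone the procedure under study. If an adverse event follows, whether it is tabulated under SAP 4.2 depends on whether the implant succeeded or, failing that, on whether the subject also had a different and more severe event. The tables then do not describe an exposed population. Every failed-attempt subject in them has a qualifying event by construction, and all other failed-attempt subjects are absent.

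The tables will be used. SAP 3.4 says that the interim report will summarise adverse event rates not related to the Solia S lead, and SAP 3 says that the pivotal analysis supports a PMA submission. Protocol 8.2.1 describes this implant as having longer procedures, longer fluoroscopy and a higher risk of septal perforation than right ventricular pacing. A regulator would expect adverse events to be summarised over everyone in whom the technique was tried.

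**Working it through.** **Step 1. What lets a failed-attempt subject in.** The protocol's description of primary endpoint 1 counts serious device effects that the CEC judges causally or probably related to the lead. It adds serious pneumothorax and cardiac perforation from the lead or its implant procedure, and deaths resulting from a lead adverse event. Events adjudicated as not related or possibly related do not count. The glossary includes septal and micro-perforation under cardiac perforation, so a serious septal perforation qualifies and a non-serious one does not.

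**Step 2. Which rule governs each event after a failed attempt, if the subject has no other qualifying event.**

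| Event | Qualifies? | Governing text | Result |
|---|---|---|---|
| Lead-related serious device effect, serious pneumothorax or perforation, lead-related death | Yes | Table 1 | In the set |
| Serious procedure event not attributed to the lead and not listed above | No | SAP 2.2.3 and 4.2 | Left out |
| Serious event adjudicated possibly lead-related | No | Not clearly in the 2.2.3 item, so SAP 3.1 | Ambiguous |
| Non-serious perforation by the lead | No | Not clearly in the 2.2.3 item, so SAP 3.1 | Ambiguous |

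After a successful implant, the subject is in all three ITT sets and the second event is tabulated.

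**Step 3. The plan's number of attempts.** For primary endpoint 2 the SAP gives 175 evaluable subjects (goal 80%, expected 88%, one-sided alpha 0.025, power 80%). The normal approximation is

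((1.96·√(0.80·0.20) + 0.8416·√(0.88·0.12)) / 0.08)² = 174.7, rounded up to 175.

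The exact test at 175 has alpha 0.020 and power 79.5%, close to plan. With 5% attrition, 175 / 0.95 = 184.2, which the SAP gives as 184.

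**Step 4. Number of failed attempts.** Protocol 8.2.1 gives 3% to 12% unsuccessful placement, and the SAP's expected 88% success implies 12%.

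- 3%: 0.03 × 175 = 5.3; 0.03 × 184 = 5.5
- 12%: 0.12 × 175 = 21; 0.12 × 184 = 22.1

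That is about 5 to 22 failed attempts. Some would be kept through a qualifying event. If that share were 7% (an assumption, borrowed from the 93% SADE-free rate expected overall), 5.3 × 0.93 = 4.9 to 22.1 × 0.93 = 20.5 subjects would be outside the set.

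The count grows with enrolment. Since enrolled means successfully implanted, 260 enrolled would imply 260 / 0.97 − 260 = 8.0 to 260 / 0.88 − 260 = 35.5 failed attempts.

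**Step 5. Effect on a percentage (illustration only).** Take 175 attempts, 154 successful and 21 failed, and assume that 10% of successes have an adverse event. Ignoring the few failed-attempt subjects kept, the table shows 15.4 / 154 = 10.0%.

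| Assumed risk in failed attempts | Failed-attempt subjects with an event | All attempts |
|---|---|---|
| 5% | 1.05 | 16.45 / 175 = 9.4% |
| 10% | 2.1 | 17.5 / 175 = 10.0% |
| 20% | 4.2 | 19.6 / 175 = 11.2% |

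The overall figure can move either way, by about a point in these cases.

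**The case against.** Four stronger readings are tempting, and the documents do not support them.

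- **That these events appear in no safety table.** SAP 4.2 is firm only for additional data of interest. SAP 3.1 could be read as the primary endpoint 2 set, which holds every failed attempt. The protocol text available starts partway through the primary endpoint 1 description, so its adverse event section, including the Section 5.1 cited in 6.1, could not be checked for a separate listing.
- **That only a SADE admits a failed-attempt subject.** The gate also covers serious pneumothorax, serious perforation and lead-related death, so some of the gravest procedural harms are kept.
- **That harm is understated.** No document gives adverse event rates by implant outcome. The comparison in Protocol 8.2.1 is with right ventricular pacing, and the limit of five placement attempts in 8.2.2 is not specific to failures. Under the glossary, an implant attempt needs only septal contact with intent to place the lead. Failed-attempt subjects also exit, so their follow-up may be short and their percentage with an event low.
- **That a primary result is biased by SAP 4.2.** Primary endpoint 1 has its own rule, and the success criterion in SAP 3.5 does not use these tables.

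It can fairly be added that the tables are descriptive and that many omitted subjects may have had no event. These objections narrow the point but do not remove it: nothing in the text available restores to the SAP 4.2 tables the events that its stated rule leaves out.

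**Conclusion.** The point holds in this limited form. SAP 4.2 and Table 1 together leave non-qualifying adverse events of failed-attempt subjects out of the additional safety tables, while the same events are counted after success. This is clear for events not related to the lead. For lead-related events that do not qualify, the defect is an unnamed denominator in SAP 3.1.

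About 5 to 22 subjects are affected per 175 to 184 attempts, less those kept through a qualifying event. This rests on the protocol's 3% to 12% failure range applying here. The number of omitted events and the direction of any change are unknown. This is a reporting gap worth closing before the pivotal report, not a threat to the study's conclusions.

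**What to change.** - In SAP 4.2, assign adverse event tables to the primary endpoint 2 ITT set, which holds all subjects with an implant attempt and is already used there for lead implant information.
- In SAP 3.1, name that set as the denominator for adverse event percentages and subject-year rates.
- Count failed-attempt subjects' events and follow-up time up to exit.
- Show successful and unsuccessful attempts in separate columns, so that the short follow-up of the latter does not blur the former.

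The cost is a few lines of SAP text and a change of analysis set. Reported events that may relate to the lead or the implant procedure already go to the CEC under Protocol 9.3. For unrelated events, the sponsor should confirm that sites report them up to exit after a failed attempt. The downside is that failed-attempt subjects add little follow-up, and the overall percentages may shift slightly in either direction.

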4.3 Subgroup Analysis

A sub-group analysis evaluating impact of age at consent (< 65 years, ≥ 65 years) may be conducted for the primary and secondary endpoints after all patients have completed the 12-month study visit. As the purpose of this analysis is to evaluate the impact of age on the outcomes, there is no formal hypothesis for this subgroup analysis.

4.4 Poolability Analysis

Poolability analyses will examine the heterogeneity of the primary endpoints across clinical sites within the U.S. and across regions (U.S. and outside of U.S.). For each analysis, sites with less than 5 subjects enrolled will be combined into one or more pseudo-sites for purposes of analysis. Starting with the site with the lowest enrollment, subjects will be successively combined into one or more pseudo-sites until the total number in each pseudo-site is not greater than the median enrollment of sites with greater than 5 subjects enrolled.

The significance of differences in rates for primary endpoint 1 and primary endpoint 2 between U.S. sites will be initially tested using a Kruskal-Wallis test statistic, with an associated p-value of 0.15 or less considered evidence of site differences. In addition, a Cochran-Mantel-Haenszel test with continuity adjustment will be used to assess the poolability across sites. If evidence is found of site differences, then the reasons for the differences will be explored using Cox and logistic regression methods to determine if any baseline subject risk factors are explanatory.

Once U.S. site poolability is confirmed, the analysis will be repeated to test region poolability (U.S. and outside of U.S.) for primary endpoint 1.

Poolability analysis will occur after analyses for the primary endpoints has been completed.

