2.2.1 Primary Endpoints

Primary Endpoint 1: Serious adverse device effect (SADE)-free rate through 3 months post-implant

The purpose of primary endpoint 1 is to evaluate the overall incidence of serious Solia S LBB lead related adverse device effects and serious implant procedure events related to the Solia S LBB lead that occur through 3 months post-implant. The parameter of interest is the Solia S LBB lead complication-free rate, which will be calculated as the number of subjects without one or more complications divided by the total number of study subjects successfully enrolled and subjects undergoing an unsuccessful implant attempt who have a qualifying primary safety endpoint event in percent.

Primary Endpoint 2: Implant success

The purpose of primary endpoint 2 is to evaluate the implant success rate of the Solia S lead in the LBB area. The parameter of interest is the percentage of subjects with Solia S placed successfully in the LBB area divided by the total number of consented study subjects in whom an implant of Solia S in the LBB area was attempted. The definition of implant success is provided in Section 4.1.2.

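### The SAP's pseudo-site rule sizes sites by subjects enrolled, defined in Table 1 as successful implants, so for implant success the grouping depends on the outcome tested and can dilute a poor site.

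*SAP*

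**What the plan says.** SAP Section 4.4 applies one grouping rule to every poolability analysis, primary endpoint 2 included: "sites with less than 5 subjects enrolled will be combined into one or more pseudo-sites for purposes of analysis". The order of merging and the size limit use the same count. "Starting with the site with the lowest enrollment, subjects will be successively combined into one or more pseudo-sites", and this continues "until the total number in each pseudo-site is not greater than the median enrollment of sites with greater than 5 subjects enrolled". A Kruskal-Wallis p-value of 0.15 or less is taken as evidence of site differences and leads to exploratory regression. The section gives no other measure of site size.

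The explicit definition of enrolled is in SAP Section 3.2, Table 1: "all enrolled subjects (subjects with successfully implanted Solia S in the LBB area". For primary endpoint 2 the table adds a second, separate group, "subjects with an unsuccessful implant attempt of the Solia S in the LBB area". SAP Section 2.2.1 makes the same split in the primary endpoint 1 denominator: "total number of study subjects successfully enrolled and subjects undergoing an unsuccessful implant attempt who have a qualifying primary safety endpoint event". The primary endpoint 2 rate is the number of successful placements "divided by the total number of consented study subjects in whom an implant of Solia S in the LBB area was attempted".

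**The concern.** For primary endpoint 2 the unit of analysis is the attempt and the outcome is success. If enrolled means successfully implanted, the variable that decides which sites are merged is the numerator of the rate being compared. Two sites with equal numbers of attempts are handled differently because one had more failures.

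At stake is how well the site comparison can detect a poorly performing site. Such a site is the one most likely to fall below 5 successes and be averaged with other small sites before the test is run. If the test then gives p above 0.15, the plan does not go on to explore reasons for site differences.

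**Working it through.** **The plan's own figure.** Section 4.4 states no calculated figure. The nearest is the primary endpoint 2 sample size (SAP 4.1.2: goal 80%, expected 88%, one-sided alpha 0.025, power 80%). The normal approximation gives n = [(1.960 × √(0.80 × 0.20) + 0.842 × √(0.88 × 0.12)) / 0.08]² = 174.7, so 175 as stated, and 175 / 0.95 = 184.2, stated as 184. The present point does not change it.

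**Attempts per site.** SAP 2.2 allows up to 25 U.S. sites. 175 / 25 = 7.0 and 184 / 25 = 7.4. If all 260 subjects were successful implants in this study at an 88% rate, 260 / 0.88 / 25 = 11.8. With all 25 sites active the average is therefore about 7 to 12 attempts. At 7 attempts, three failures leave 4 successes, which is below the threshold.

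**Chance that a site with 5 or more attempts is classed as small.** With m attempts and true success rate p, this is P(X ≤ 4) for X ~ Binomial(m, p).

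| Attempts | p = 88% | p = 60% | p = 50% | p = 40% |
|---|---|---|---|---|
| 7 | 4% | 58% | 77% | 90% |
| 8 | 1% | 41% | 64% | 83% |
| 10 | under 0.1% | 17% | 38% | 63% |
| 12 | under 0.1% | 6% | 19% | 44% |

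Sized by attempts, every entry is 0. At a common rate of 88%, the 7-attempt sites that fall below 5 successes have an expected observed rate of 55%, so the rule selects on outcome.

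**How merging dilutes (assumed layout).** Take thirteen sites with 12 attempts and 143 successes in total, one site with 3/8, and two with 3/3. Overall this is 152/170 = 0.894. On binary data a site with s successes in n attempts contributes (s − 0.894n)² / [n × 0.894 × 0.106] to the Kruskal-Wallis statistic, before the factor (N − 1)/N.
- By attempts: 3/8 stands alone and contributes 22.8. The two 3/3 sites form 6/6 and contribute 0.7. The sum is 23.5, with 15 groups.
- By successes: the three sites form 9/14 and contribute 9.3, with 14 groups.

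The p-value also depends on how the 143 successes are spread. Over the seven splits with 10, 11 or 12 successes per site, p is 0.002 to 0.044 by attempts (always flagged) and 0.08 to 0.68 by successes (flagged in two of seven).

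**Power to flag at p ≤ 0.15 (simulation, with the median treated as a cap).**

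| Assumed layout | By attempts | By successes |
|---|---|---|
| 13 sites × 12 attempts at 90%, two 3-attempt sites, one 8-attempt site at 40% | 0.82 | 0.60 |
| Same, poor site 10 attempts at 60% | 0.51 | 0.49 |
| Same, poor site 12 attempts at 40% | 0.91 | 0.90 |
| 25 sites × 4 to 11 attempts at 91%, one 8-attempt site at 40% | 0.78 | 0.71 |
| Same, two 8-attempt sites at 50% | 0.84 | 0.81 |
| Same, three 8-attempt sites at 60% | 0.75 | 0.70 |
| 25 sites, all at 88% (no true difference) | 0.13 | 0.14 |

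If no other small site exists to merge with, the first layout gives 0.81 under both rules.

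**The case against.** The strongest reply is that enrolled is not a fixed term in this SAP. Section 4.1.2 speaks of enrolling 184 patients to evaluate primary endpoint 2, whose denominator is attempts. Section 4.1.1 calls all 157 subjects of the other study enrolled, although that study covered both His bundle and LBB area implants. If Section 4.4 meant each endpoint's analysis population, the problem disappears. This stands as a reason to call the point conditional. It does not remove it, because the explicit definition in Table 1 says otherwise and a programmer following the SAP would use it.

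Second, the larger losses need a particular combination: a site with few attempts, a very low true success rate, and other small sites to merge with. No published success rate in SAP Table 3 is below 87.9%, and protocol Section 8.2.2 says implanters are chosen for experience. This also stands and limits the size of the effect.

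Third, the section also plans a Cochran-Mantel-Haenszel test, reasons for failed placement are reported (SAP 2.2.3), and monitoring includes trend analyses (protocol 10.1). So the Kruskal-Wallis test is not the only safeguard. However, the Cochran-Mantel-Haenszel test sits under the same grouping rule, and the other two are not formal comparisons of sites.

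Some stronger readings might be inferred, and the documents do not support them:
- That the stopping rule, read literally, combines nothing. The preceding sentence says small sites are combined, and "not greater than the median enrollment of sites with greater than 5 subjects enrolled" is evidently meant as a cap, though loosely worded.
- That the test is generally biased toward declaring sites poolable. With no true differences the flag rate is essentially the same under both rules.
- That poor sites are removed from the analysis. Their failures stay in the test and are only averaged with other sites, and a site with 5 or more successes is never merged.

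**Conclusion.** The point holds on the Table 1 definition of enrolled. Section 4.4 then groups sites for primary endpoint 2 by the numerator of the outcome under test and loses some power to flag a poor site. The loss is about 2 to 7 points in most assumed layouts, near zero where the poor site has many attempts or has no small sites to join, and about 20 points for one 8-attempt site at 40% with other small sites present. The merge probabilities follow from the binomial alone. The power figures rest on assumed site sizes and success rates that the documents do not give.

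A reader might infer that the primary endpoint 2 conclusion is at risk. It is not: that test, its population, alpha and sample size do not use the pseudo-sites, and the poolability analysis comes after it. That timing is still a reason to settle the wording now, since otherwise the meaning of enrolled would be decided with outcomes known.

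**What to change.** In SAP Section 4.4, define site size as the number of subjects in the ITT population of the endpoint being tested; for primary endpoint 2 that is subjects with an LBB-area implant attempt. Use this count for the threshold of 5, the order of combining and the median. In the same edit, state the median as a cap: sites with fewer than 5 such subjects are combined from the smallest upward as long as the pseudo-site total does not exceed it. Take the median over sites with 5 or more, because sites with exactly 5 are now neither merged nor counted in the median.

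The cost is an SAP wording change, which SAP Section 5 provides for before study completion, using counts already collected. The downside is that a site difference may be declared slightly more often and then need exploring.
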